5.0 STUDY TREATMENT

5.1 Dosing and Administration

Dispersible zinc sulfate tablet (10 mg) or identical placebo tablet, manufactured by Laboratoires Pharmaceutiques Rodael, France, and imported from India by Uganda Health Marketing Group. Tablet regimens of 30 tablets will be packaged and distributed in air tight containers to prevent moisture contamination. These tablets are currently available in Uganda, are certified as manufactured under good manufacturing process (GMP). The use of tablets currently available on the market will allow for easy implementation of the intervention if successful. Each tablet is designed to dissolve completely in a small amount of water or breast milk in <3 minutes, removing the need for small children to swallow a pill. Caregivers will be instructed to place the pill in 5-10 mL of clean water or breastmilk, stir gently, and wait three minutes until the pill is completely dissolved. Both active tablets and placebo will have the same flavoring added to enhance palatability.

5.2 Side Effects

The primary side effect of zinc is vomiting, and it is infrequent. For children who do have problems with vomiting, parents will be told to give the zinc with food, as this practice can decrease vomiting. Long term, zinc can decrease copper levels. We will check copper levels from samples at baseline and 12 months, to see if copper levels are affected in children in the ZIPS study.

5.3 Study Discontinuation and Stopping Rules

Data from this study will be reviewed in real-time by the Principal Investigator and Co-Investigator team members. Data will be reviewed periodically with an external DSMB. ZIPS will be discontinued if at any time the DSMB or study team feels that it is in the best interests of study subjects to do so.

6.0 STUDY ASSESSMENTS AND STUDY PROCEDURES

In addition to zinc or placebo prescribed at fixed doses as described above, procedures to be performed as part of the data collection and analysis for the ZIPS Study are detailed in this section and summarized in the Study Evaluations SOP.

6.1 Baseline and Follow Up Visit Sample Collection and Clinical and Lab Assessment

At baseline, children will have a history and physical exam performed, relevant history related to SCA obtained, including prior history of stroke, transfusions, and hospitalizations. Age, sex, height, weight and geographical area where the child lives will be recorded. At baseline and 12 month visits, 7 ml of blood will be obtained for a CBC with differential and reticulocyte count, and hemoglobin electrophoresis, and plasma, whole blood and filter paper dried blood spots samples obtained and stored. 5 ml of blood will be drawn at the 6 month visit for plasma, whole blood and filter paper dried blood spot samples. Plasma, blood and filter paper samples will be stored because some testing cannot be done immediately but only when all samples are collected, and also because new literature often shows novel factors that may relate to risk of infection or micronutrient deficiency, so we may test for these in future studies. We will assess genetic and immune risk factors, including variants of sickle cell disease and factors such as heme oxygenase-1 polymorphisms, that may affect the clinical course of sickle cell disease or response to infection, and will also store samples to look for novel genetic factors discovered in the course of the study that may relate to risk of infection, micronutrient deficiency or adverse effects from sickle cell disease.

Socio-economic status and dietary history will be assessed by a previously validated tool. An instrument for dietary history developed and validated in other child health studies in this area will be used to assess child diet, and this will be reassessed at 12-month follow-up. The instrument includes assessment of foods rich in zinc and assessment of pica. Other variables assessed will include other medications taken that are not standard MHSCC administered medications, and HIV infection (children will be tested unless parents elect not to have testing).

Urine samples will be collected in zinc-free containers at enrollment and 12-month follow-up in 100 randomly selected children to test for urine zinc levels, to assess degree of urinary zinc loss in study children at baseline and after 12 months of zinc or placebo treatment. This data will provide valuable new information about the degree of zinc lost in the urine in African children <5 years of age. Stool samples will also be collected from children who are able to provide them, for future microbiome testing.

6.2 Follow Up Clinical and Lab Assessments and Treatment for Acute Illness

Children in the study will have follow up visits at 1, 3, 6, 9 and 12 months. The visits will allow replenishment of zinc or placebo tablet supply, assess adherence (by pill counts), and evaluation of adverse events. They will also allow interim measurements of height and weight. Parents or guardians will be asked to bring their children to the NSCC for any illness. All care during the study will be provided without cost, and with reimbursement for transportation. A full list of study evaluations and testing is provided in the Study Evaluations SOP.

Children with illness will be evaluated clinically and all illnesses recorded on a sick visit case report form (CRF). Children will be managed according to the SCC treatment protocols developed at the Mulago

National Referral Hospital Sickle Cell Clinic. Definitions will be provided for the most common infections, which will be listed on the CRF, and any other infections will be entered as free text diagnosis. Children with pneumonia/acute lower respiratory tract infection (ALRI) will have a swab collected for later testing by nasopharyngeal swab PCR for *Mycoplasma pneumoniae*, *Chlamydomphila pneumoniae*, *Bordetella pertussis* and 17 viral upper respiratory infection (URI) pathogens. We are not able to do testing in real time, but treatment with a macrolide antibiotic is part of standard of care for children with pneumonia/ALRI. For this study children who have clinical signs of pneumonia (see Appendix I) will receive a chest x-ray to confirm the diagnosis of pneumonia. Other labs will be collected as needed for clinical diagnosis, and a blood sample collected and stored for future infectious pathogen or inflammatory response testing.

6.3 Standard Infection Prevention and Other Preventive Care in Children with SCA

Current standard of care for infection prevention per the Mulago Hospital Sickle Cell Clinic (MHSCC) guidelines for Ugandan children under 5 years of age with SCA includes immunization with pneumococcal 13-valent conjugate vaccine in infancy, penicillin prophylaxis until age 5 years to prevent pneumococcal infection, and sulfadoxine-pyrimethamine monthly prophylaxis to prevent malaria. Children also receive daily folic acid to decrease risk of anemia. We will provide any vaccinations, medications or supplements that a child requires and has not received. To these standards, we will add provision of an insecticide-treated bednet for all children, to further decrease risk of malaria.

Hydroxyurea therapy. We recently completed the blinded phase of the NOHARM study, a placebo-controlled study of hydroxyurea safety and efficacy in children with SCA at the MHSCC, which is in Kampala, Uganda. The data suggest that hydroxyurea therapy was both safe and effective in these children²⁰, but they live in an area of much lower malaria transmission than the children at Jinja Regional Referral Hospital. There are currently no national guidelines on hydroxyurea therapy, and Mulago Hospital Sickle Cell Clinic guidelines provide an outline of children who may benefit from therapy (e.g., children who have had stroke, or have had more than 3 pain crises requiring hospitalization), but recommend that any decision should be made individually by a sickle cell clinic clinician. For this reason, for the ZIPS study, until national guidelines on hydroxyurea are available, the Nalufenya Sickle Cell Clinic (NSCC) clinicians will decide which children should receive hydroxyurea therapy, based on clinical history, and will monitor the child for adverse events if placed on hydroxyurea therapy. If hydroxyurea is prescribed by clinic physicians but cannot be afforded by the child's family during the study, the study will facilitate covering hydroxurea costs for the duration of the study. If hydroxyurea is given, it will be assessed as a covariate in analyses.

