2.0 SPECIFIC AIMS

The **specific aim** of the study is to determine if zinc supplementation reduces severe or invasive infections in Ugandan children 1.00-4.99 years of age with SCA.

The study will also assess **four secondary outcomes** that may be affected by zinc supplementation in children: 1) incidence of all clinically diagnosed infections; 2) incidence of culture or PCR-confirmed bacterial infections, 3) incidence of vaso-occlusive crises (VOC), and 4) change in height-for-age z-score. We hypothesize that children with SCA who receive zinc supplementation will have less clinical infections, less culture or PCR-confirmed bacterial infections, less VOC and better growth than children who receive placebo.

The primary study goal is assessment of severe or invasive infection, and the study is powered for that outcome. However, information on differences of confirmed bacterial infection, VOC, and growth will provide important preliminary data for future studies. Finally, the study will assess the **frequency of**

adverse events with zinc, with particular attention to nausea and vomiting, the most common side effects seen with zinc supplementation.

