4.11 Secondary Outcomes

1) Clinical infection: as described above: 2) Culture confirmed bacterial infection (e.g., bacteremia, urinary tract infection, tonsillitis, abscess, osteomyelitis, meningitis) or PCR-confirmed infection with *Chlamydomphila pneumoniae* or *Mycoplasma pneumoniae* (from nasopharyngeal swab) in children with pneumonia/acute chest syndrome. Pneumonia (acute lower respiratory infection, ALRI) will be defined as: history of fever or measured axillary temperature $\geq 37.5^{\circ}\text{C}$, with age-specific tachypnea, cough, and an infiltrate and/or effusion on chest x-ray consistent with pneumonia (see Appendix II for full definition).

2) *Vaso-occlusive crises (VOC)*: pain with the requirement for oral morphine or IM diclofenac, per SCC guidelines.

3) *Change in height for age z-score*, from enrollment to 12 months follow up, calculated using WHO standards.

4) *Serious adverse events*: 1) death; 2) a life-threatening event; or 3) hospitalization > 7 days.

5) *Adverse events*: based on CTCAE criteria, with modifications for SCA, as in the NOHARM study, will be assessed at the 1, 3, 6, 9 and 12-month follow-up visits, and at all sick visits.

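### Hydroxyurea started after randomisation may enter the zinc comparison as a covariate; covariates should be limited to values measured before randomisation

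*Combined protocol and SAP*

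**What the plan says.** Section 6.3 has no national hydroxyurea guideline to follow. It reports that the Mulago clinic guidelines "recommend that any decision should be made individually by a sickle cell clinic clinician", with stroke, or children who "have had more than 3 pain crises requiring hospitalization", as example grounds. For this trial, until national guidelines exist, the clinic's "clinicians will decide which children should receive hydroxyurea therapy, based on clinical history". Prescription during the study is foreseen: where a family cannot pay, "the study will facilitate covering hydroxurea costs for the duration of the study". The paragraph ends: "If hydroxyurea is given, it will be assessed as a covariate in analyses".

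Section 9.2 compares infection incidence by Poisson or negative binomial regression, adds further factors potentially related to infection risk as covariates, and repeats similar models for confirmed bacterial infection, vaso-occlusive crises (VOC), SAEs and AEs. It lists no covariates, sets no baseline limit and names no unadjusted regression. It does also plan chi-square comparisons of frequencies.

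Section 2.0 hypothesises that children on zinc will have "less clinical infections, less culture or PCR-confirmed bacterial infections, less VOC and better growth than children who receive placebo". Section 4.11 defines VOC as "pain with the requirement for oral morphine or IM diclofenac, per SCC guidelines", with no hospitalisation requirement.

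**The concern.** Hydroxyurea use at enrolment is a legitimate covariate. A start after randomisation is different. Clinicians decide on the child's history, repeated hospitalised pain crises are a named example ground, and the study removes the cost barrier. If zinc lowers crises or infections, fewer zinc children will reach the point at which hydroxyurea is started, and those who do will be sicker.

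Conditioning on the start then compares unlike children. Among children who never start, placebo has lost more of its severe cases than zinc has. Among those who start, zinc children needed higher underlying severity to get there. Both push the zinc rate up relative to placebo. Blinding does not prevent this, because starts follow events rather than knowledge of the arm.

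At stake is what the rate ratio means: it would no longer be the effect of assignment. The secondary VOC model is more exposed, because there the event that prompts a start is the outcome itself.

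**Working it through.** **The plan's own figures (9.1, 9.2).** Placebo rate 0.71/year, rate ratio 0.60, 125 per arm, 10% loss, two-sided alpha 0.05.

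- Child-years per arm after loss: 125 × 0.90 = 112.5. Expected events: 112.5 × 0.71 = 79.9 and 79.9 × 0.60 = 47.9.
- Power = Φ(|ln 0.60| / √(1/79.9 + 1/47.9) − 1.96) = Φ(0.511/0.183 − 1.96) = 79.8%, which matches the stated 80%.
- Events without loss: 125 × 0.71 × 1.60 = 142, as stated.

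These figures are not in dispute. The plan gives no figure for the covariate question, so it has to be modelled.

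**Model (assumptions unless sourced).** Each child has a log-normal severity with mean 1 and log-scale SD 0.7, shared by VOC and infection. The placebo infection rate is 0.71/year (9.1) and the true zinc infection rate ratio is 0.60 (9.2). Placebo VOC rate is 1/year and the zinc VOC rate ratio 0.6. Hydroxyurea has no effect of its own. A start occurs at the 4th hospitalised crisis within the year (the example in 6.3 is more than 3). The fitted model is Poisson, log E(events) = a + b·zinc + c·hydroxyurea, and the adjusted ratio is exp(b). Hydroxyurea is coded either as an ever-started indicator or as time-varying. Expected totals were computed exactly and agree with simulation of 2,000,000 children per setting to within 0.004.

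**Infection rate ratio, truth 0.60, trigger as in 6.3**

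| Setting | Ever-started | Time-varying |
|---|---|---|
| All VOC hospitalised | 0.639 | 0.613 |
| Half hospitalised | 0.610 | 0.603 |
| 30% hospitalised | 0.603 | 0.601 |
| All; zinc VOC ratio 0.8 | 0.621 | 0.607 |
| All; severity SD 0.35 | 0.606 | 0.601 |
| All; 0.5 VOC/year | 0.610 | 0.603 |
| All; 2 VOC/year | 0.693 | 0.637 |
| All; no severity variation | 0.600 | 0.600 |

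In the first row 4.7% of placebo and 1.4% of zinc children start: 0.047 × 125 ≈ 6 against 0.014 × 125 ≈ 2. If zinc has no effect on infection but does reduce VOC, 1.00 becomes 1.066, 1.017 or 1.005 (all, half or 30% hospitalised, ever-started).

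**Scale.** The shift is ln(0.639/0.60) = 0.063. With the same severity, overdispersion is exp(0.49) − 1 = 0.632, and the SE of the log ratio is √((1/0.71 + 1/0.426 + 2 × 0.632)/112.5) = 0.211. So the shift is 0.063/0.211 = 0.30 SE. With half hospitalised it is ln(0.610/0.60)/0.211 = 0.08 SE.

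**VOC as outcome, truth 0.60, ever-started.** 0.702, 0.623 or 0.606 (all, half or 30% hospitalised). With all hospitalised and no severity variation it is still 0.635, so this bias needs no shared severity.

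**Starts also prompted by a third infection (not documented).** Ever-started: 0.744 (all hospitalised) or 0.732 (half). If zinc has no effect on VOC: 0.658 or 0.708. Time-varying coding gives 0.611 to 0.621 throughout.

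**Different model.** With gamma frailty (variance 0.5 to 1.0), monthly steps and starts prompted by infections, 0.60 becomes 0.60–0.61 when 2% of placebo children start, 0.63–0.64 at 7% and 0.70–0.72 at 18–19%.

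**Where there is no bias.** Starts unrelated to arm leave 0.60 at 0.60. If zinc changes neither VOC nor infection, 1.00 stays 1.00. Absence of an effect on VOC alone is not enough if infections also prompt starts.

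**The case against.** The strongest reply is that the effect is small and the text does not commit to it. Assessing hydroxyurea as a covariate names neither the primary model nor an ever-started coding, and it could mean enrolment use or a supportive analysis. The 0.64 case needs every VOC hospitalised, although the definition in 4.11 does not require admission. With half hospitalised about one placebo child and no zinc child would start, and time-varying coding gives 0.60 to 0.61. The larger figures rest on an infection trigger or a crisis rate that the documents do not contain. Some starts would be unrelated to arm: those based on history before enrolment, or those following a new national guideline in calendar time, which blocks of 8 by order of entry would balance. The bias does not manufacture a benefit for zinc. The chi-square comparisons in 9.2 are by arm and free of hydroxyurea.

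Most of this stands as a statement about size. Two points limit it. Counting crises before enrolment towards the trigger brings more children near it: with two prior years assumed, the ratio is about 0.61 to 0.63 over the same range of hospitalised fractions. And the chi-square tests compare frequencies; they do not supply the rate ratio on which the trial's hypothesis is stated. That the wording permits several readings is the reason to settle it before the data are seen.

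**Conclusion.** The concern holds. As written, 6.3 and 9.2 allow the zinc comparison to be adjusted for a variable that assignment can change, and the adjusted ratio then does not estimate the effect of assignment. With the example trigger in 6.3 and up to 1 VOC/year, the primary ratio moves from 0.60 to between 0.60 and 0.64, at most about 0.3 of a standard error. At 2 VOC/year, all hospitalised, it reaches 0.69. The secondary VOC ratio moves from 0.60 to between 0.61 and 0.70. In every scenario run the shift is towards the null or against zinc. It is negligible if starts are rare and absent if zinc affects none of the events that prompt them.

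Uptake, VOC rate, hospitalised fraction and severity spread are all assumed, so the size cannot be fixed from the documents. The problem of definition does not depend on the size. The change should be made because it is nearly free, not because a large bias has been shown.

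**What to change.** - **Section 9.2:** for the treatment-comparison models, replace the open reference to other factors with factors measured before randomisation.
- **Section 6.3:** name hydroxyurea use at enrolment as the covariate.
- **Estimate and reporting:** keep the primary estimate by randomised arm regardless of later hydroxyurea, report on-study starts by arm, and label any analysis adjusting for on-study hydroxyurea as supplementary.
- **Data:** confirm that hydroxyurea start dates are captured. Section 6.1 records medications only in general terms ("Other variables assessed will include other medications taken that are not standard MHSCC administered medications"), and the Study Evaluations SOP is not among the documents. Add a CRF field only if the dates are missing.

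The cost is one sentence in each section, plus possibly one CRF field. Any apparent precision from post-baseline adjustment is given up. Nothing changes about who receives hydroxyurea or when.

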6.4 Testing Methods

Plasma and urine zinc testing and plasma copper testing. At study completion, plasma zinc and copper levels and urine zinc levels will be tested in the baseline and 12 month samples at the Wright Lab at Mount Sinai Hospital, New York, New York or a similarly certified lab for zinc testing. Blood and urine samples will be collected using a tight trace metal specific sample collection protocol to minimize contamination.

Hemoglobin electrophoresis will be done using standard capillary electrophoresis techniques on fresh samples or thawed samples stored for <6 months.

PCR testing of NP swabs for C. pneumoniae, M. pneumoniae, B pertussis and 17 viral URI pathogens. Nasopharyngeal (NP) swab specimens will be analyzed using the FilmArray[®] Respiratory Panel (RP; BioFire Diagnostics, Salt Lake City, UT) by collaborators at the Indiana University Health Pathology Laboratory (IUHPL) in Indianapolis, IN.

Microscopy testing for malaria. Microscopy for *Plasmodium* species by thick and thin smear, with parasite quantification, will be performed as previously described²¹, with a minimum of two independent readings.

7.0 DATA MANAGEMENT

7.1 Introduction

Clinical trial management systems (CTMS) utilizing standard database programs are widely utilized in clinical research centers across the US and internationally. These systems provide a platform for electronic protocol management (including regulatory affairs and clinical quality assurance monitoring), billing compliance, data management/EDC functionality, as well as biospecimen and registry/repository management. The study will use a database to enter, clean and store data.

All study personnel will be trained in the study protocols. The clinical staff shall record the data from the patients into study forms. Laboratory results shall also be recorded into study forms. All study forms will be brought to the data room and entered into databases. All laboratory results will be entered into similar databases. These relational databases allow merging of data from the numerous separate data tables. Each study participant shall have a file that will contain all the study related source documents for the child. These files and other data sheets will be kept in file cabinets in the data room. The data room will be accessible by study personnel only. The data room will be locked securely any time staff members are not present. Databases will be kept on password-protected computers accessible only to authorized study personnel.

7.2 Data Security and Validation

The study database will be password protected, backed up in real-time, and allows for audit trail review. The data management team, after the appropriate documentation will assign credentials and security privileges based upon the individual roles and specifications appropriate to the protocol. These privileges also impact the information that is viewable by the user(s), which allows for securing of protected health information (PHI) as well as ensuring that protocol de-identification or blinding procedures are followed from a data standpoint.

7.3 Protocol Deviations

In the event that an unanticipated or unintended alteration/action occurs, different from what is expected from this study in regards to the protocol, consent documents, or study addenda, it is deemed a protocol deviation. A protocol deviation log will be maintained within the study database and at the study site. Protocol deviations will be filed with the ethical review boards.

8.0 SAFETY ASSESSMENT AND REPORTING

8.1 Adverse Event Reporting Requirements

All adverse events (AE) and serious adverse events (SAE) will be collected and reported to the Medical and Data Coordinating Center at IU using the correct data collection forms. AE reporting will utilize the Common Terminology Criteria for Adverse Events (CTCAE) Version 4.0 available since 2009, where all AE are categorized by organ system and graded by severity. A list of expected and potentially serious AE's, as well as exceptions to the CTCAE's is included in Appendix II (Tables 1 and 2).

SAE reporting will use standard definitions (any life-threatening event hospitalization or death) however, since hospitalization is common in children with SCA, we will use hospital stay of more than 7 days to define hospitalization-related SAE in this study. This is based on the knowledge that children who are admitted with sickle cell-related conditions (such as anemia requiring transfusion, acute chest syndrome, and stroke) have an average length of stay of approximately 7 days. A SAE for this study will therefore be defined as: 1) hospitalization for more than 7 days; 2) any other life-threatening event* (based on clinician judgement); or 3) death. All SAEs will be followed until resolution or stabilization.

All SAEs will be reported via email to the in-country principal investigator or an assigned representative within 48 hours of the staff becoming aware of it, using an SAE form, which should be completed, scanned and sent electronically. The SAE form asks for nature of event, date of onset, severity, corrective therapies given, outcome and causality (i.e. unrelated, unlikely, possible, probably, definitely). The responsible study clinician should assign the causality of the event. Additional information will be sent within 14 additional days (full SAE report) if the condition has not resolved at the time of e-mail notification.

SAEs will be reported to the primary site IRB (Makerere University School of Medicine Research Ethics Committee) within 7 days of the team being aware of the SAE. Complied SAE logs will be sent to the Uganda National Drug Authority (NDA) in quarterly reports, and to the study IRBs and DSMB annually or as requested by those organizations.

*Life-threatening in the definition of a serious adverse event or serious adverse reaction refers to an event in which the subject was at risk of death at the time of the event. It does not refer to an event which hypothetically might have caused death if it were more severe.

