10.4 Data and Safety Monitoring Board (DSMB) and Stopping Rules

The DSMB will consist of 4 individuals, Drs. [name] (pediatrician, nutrition expert), [name] (pediatrician, malaria and sickle cell research expert), [name] (pediatrician, clinical sickle cell care and research expert) and [name] (biostatistician). The DSMB will meet every 6 months via Skype or other teleconference. The DSMB will review the data and provide guidance on study conduct and continuance. DSMB members will be independent and look at the trial from an ethical point of view of the participant safety, future patients and society in general. It is the responsibility of the DSMB to prevent patients being exposed to any excess risks by recommending to the study team and sponsors for trial suspension or termination early if SAEs appear to differ between study groups. The trial statistician will be invited to attend part of the DSMB meeting to present the most current data from the trial. This will be blinded, unless the DSMB specifically requests an unblinded analysis. If an unblinded analysis is requested by the DSMB, it will be provided to them and not to study personnel. Each DSMB member will be expected to serve for the duration of the trial. If a member is unable to continue participation, the reason will be documented and a replacement will be selected by the sponsor.

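### The SAE definition has no disability criterion and no exception for drug-related admissions, so some serious non-fatal events with stays of 7 days or less are handled only as AEs

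*Combined protocol and SAP*

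**What the plan says.** Section 8.1 opens its SAE paragraph by invoking standard definitions, but names only life-threatening events, hospitalization and death. It then narrows the second of these: "we will use hospital stay of more than 7 days to define hospitalization-related SAE in this study". Two reasons are given. Admission is common in sickle cell anemia, and children admitted with sickle cell-related conditions, "such as anemia requiring transfusion, acute chest syndrome, and stroke", are said to "have an average length of stay of approximately 7 days". The resulting list is closed at three items: a stay of more than 7 days, and in addition only "2) any other life-threatening event* (based on clinician judgement); or 3) death". A note to section 8.1 reads life-threatening narrowly, as actual risk of death when the event occurred.

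Section 4.11 makes SAEs a secondary outcome on the same terms: "1) death; 2) a life-threatening event; or 3) hospitalization > 7 days". Section 10.4 asks the DSMB to recommend "trial suspension or termination early if SAEs appear to differ between study groups". It proposes a trigger that compares the intervention group's SAE rate with the 95% confidence limits of the control group's rate.

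Events that are not SAEs are still collected and graded by CTCAE (section 8.1). They are assessed at months 1, 3, 6, 9 and 12 and at sick visits (section 4.11), and compared between arms (section 9.2).

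**The concern.** There are two gaps in the definition.

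1. **Disability.** No criterion covers lasting harm as such. Section 8.1 describes the list in Appendix II as containing potentially serious events, and Table 1 there includes stroke, hemiplegia and cognitive dysfunction. The SAE definition reaches these only through risk of death or a long stay.
2. **Drug-related admissions.** The reason for the 7-day cut is the frequency and usual length of sickle cell admissions. The cut is applied to every admission. Vomiting is the primary side effect of zinc according to section 5.2 and a named focus of safety assessment in section 2.0, but it does not appear in Table 1. The stated reason does not extend to it.

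What is at stake is how such events are handled while the trial runs. Prompt reporting, the written causality assessment and the proposed numerical safety trigger are all attached to SAEs.

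**Working it through.** **Step 1. The plan's own figure.** The only number behind the threshold is the average stay of about 7 days in section 8.1. It cannot be reproduced. The documents give no length-of-stay data, no spread and no figure by condition.

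**Step 2. Apply the definition as written (sections 8.1 and 4.11).**

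| Event | Stay over 7 days? | Risk of death at the time? | Fatal? | Class |
|---|---|---|---|---|
| Stroke, judged life-threatening, short stay | no | yes | no | SAE |
| Stroke with residual deficit, long stay | yes | no | no | SAE |
| Stroke with residual deficit, stay of 7 days or less | no | no | no | AE only |
| Admission possibly due to zinc, life-threatening, short stay | no | yes | no | SAE |
| Admission possibly due to zinc, stay of 7 days or less | no | no | no | AE only |

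The third and fifth rows are the gap.

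**Step 3. What the class decides.**

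| Safety step | SAE | AE only |
|---|---|---|
| Collected, graded, compared between arms (4.11, 8.1, 9.2) | yes | yes |
| SAE secondary outcome (4.11) | yes | no |
| Notice to the in-country principal investigator within 48 hours (8.1) | yes | not specified |
| Report to the primary ethics committee within 7 days (8.1) | yes | not specified |
| Causality assigned by the study clinician on the form (8.1) | yes | not specified |
| Counted in the proposed safety trigger (10.4) | yes | no |

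The causality row matters because the abstract lists zinc-related adverse events among the secondary outcomes. Section 8.1 describes a causality assessment only on the SAE form.

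**Step 4. How far the size can be taken.** Let the mean stay be m and the coefficient of variation be CV. The share of stays of 7 days or less is then:

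- log-normal: s² = ln(1 + CV²) and P = Φ[(ln 7 − ln m + s²/2)/s], which is Φ(s/2) when m = 7;
- gamma: shape k = 1/CV², scale m/k, and P = the gamma distribution function at 7.

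Examples at m = 7 and CV = 1: log-normal s = √(ln 2) = 0.833, so P = Φ(0.416) = 0.661; gamma (here exponential) P = 1 − e⁻¹ = 0.632.

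The CV range of 0.3 to 1.5 is an assumption and is not in the documents. Because the protocol says only approximately 7 days, m is also varied.

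| Assumed mean (days) | Share of stays of 7 days or less, across both shapes and all CVs |
|---|---|
| 6.5 | 62% to 73% |
| 7.0 | 54% to 71% |
| 7.5 | 45% to 68% |

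These shares describe the pooled group of sickle cell admissions and the length-of-stay criterion alone. They show that the cut lies near the middle of that group's stays. They do not give the share of strokes, or of disabling events, that are missed. For that one would need the stay for stroke itself and the proportion of short-stay events judged life-threatening. The documents give neither.

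**The case against.** The 7-day cut is a disclosed choice with a sensible aim, which is to keep routine sickle cell admissions from swamping SAE reporting. That stands, and the fix leaves the cut in place for admissions in general.

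A reader might infer that every short zinc-related admission is excluded. It is not: life-threatening and fatal events are SAEs whatever the stay.

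A reader might also infer that many strokes, or at least half of stroke and acute chest syndrome admissions, escape the definition. The documents do not support this. The 7-day figure is one pooled average, stroke stays may be longer than it, and even for the pooled group the share falls to 45% under one of the assumed cases.

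The strongest inference would be that a safety difference in these events would go unseen. The protocol contradicts this. All AEs are graded and compared between arms, and section 2.0 gives nausea and vomiting particular attention. The DSMB reviews the data every 6 months and may ask for unblinded results. Section 5.3 allows the trial to be stopped at any time in participants' interests. The SAE trigger in section 10.4 is itself only proposed, with final rules to be settled with the DSMB.

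These points limit the consequence but do not remove it. General AE capture supplies neither the prompt reporting nor a place in the SAE rate, and a disabling event counted among all AEs carries no more weight there than a minor one.

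**Conclusion.** The gap is real and narrow. Followed as written, sections 8.1 and 4.11 class a non-fatal event that is not judged life-threatening as an AE only when the stay is 7 days or less, even if it leaves lasting disability or is thought to be due to study drug. Such an event loses its place in the SAE outcome, the expedited reporting and the proposed stopping rule. It is not lost to the trial.

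The classification follows from the text and needs no assumption. The number of events affected cannot be stated. The calculated shares rest on assumed distributions for a pooled group and should not be read as applying to stroke. The change is a cheap improvement to safety monitoring; it does not bear on the efficacy analysis.

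**What to change.** In sections 8.1 and 4.11, keep the 7-day rule for admissions in general and add two criteria:

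- (a) *persistent or significant disability or incapacity, whatever the length of stay*;
- (b) *hospitalization of any length that the study clinician assesses as possibly, probably or definitely related to study drug*, using the causality scale already on the SAE form.

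Criterion (b) needs causality to be recorded for short admissions before they are classed, so the item should also appear on the form used for them. The blinding described in section 4.8 means the judgement is made without knowledge of the arm.

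Use the same definition for the SAE rates in section 10.4, and reconcile the reference to standard definitions in section 8.1 with the list that follows it.

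Do not define the exception by whether the cause is listed in Appendix II Table 1. Malaria, diarrhea, dysentery, cellulitis, abscess and meningitis are primary-endpoint infections and are not in that table. Every admission for them would become an SAE, and the SAE rate would then carry efficacy events that could mask harm from zinc. Table 1 also lists hospitalization over 24 hours, which is not a cause and would make the test ambiguous.

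The cost is protocol wording, a check box or two, a causality check for short admissions and a few more SAE reports. No visits or procedures are added.
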